## **10.0 STUDY MANAGEMENT**

### **10.1 Institutional Review Board (IRB) Approval and Consent**

It is expected that the IRB will have the proper representation and function in accordance with federally mandated regulations. The IRB should approve the consent form and protocol.

In obtaining and documenting informed consent, the investigator should comply with the applicable regulatory requirement(s), and should adhere to Good Clinical Practice (GCP) and to ethical principles that have their origin in the Declaration of Helsinki.

Before recruitment and enrollment onto this study, the patient will be given a full explanation of the study and will be given the opportunity to review the consent form. Each consent form must include all the relevant elements currently required by the FDA Regulations and local or state regulations. Once this essential information has been provided to the patient and the investigator is assured that the patient understands the implications of participating in the study, the patient will be asked to give consent to participate in the study by signing an IRB-approved consent form.

Prior to a patient's participation in the trial, the written informed consent form should be signed and personally dated by the patient and by the person who conducted the informed consent discussion.

## 10.2 Required Documentation

Before the study can be initiated at any site, the following documentation must be provided to the Clinical Protocol Office (CPO) at the University of North Carolina.

- A copy of the official IRB approval letter for the protocol and informed consent
- IRB membership list
- CVs and medical licensure for the principal investigator and any sub-investigators who will be involved in the study.
- Form FDA 1572 appropriately filled out and signed with appropriate documentation
- Financial Disclosures
- CAP and CLIA Laboratory certification numbers and institution lab normal values
- Executed clinical research contract

## 10.3 Registration Procedures

If multicenter study use language below:

All patients must be registered with the LCCC CPO UNCCN at the University of North Carolina before enrollment to study. To register a patient call the UNCCN at [[contact]]([contact]) Monday-Friday 8:30 am – 5:00 pm EST. [contact]) or email (address to be provided at SIM) registration form, signed informed consents and all source documents to confirm eligibility. When sending registration request with eligibility documentation, please allow 24 hours for source to be reviewed.

For Affiliate patients, to register and confirm patient eligibility, please fax registration forms, informed consent, and source documents to [contact].

## 10.4 Data Management and Monitoring/Auditing

The CPO UNCCN of the UNC LCCC will serve as the coordinating center for this trial. Data will be collected through a web based clinical research platform, OnCore®. Other study institutions will be given a password to directly enter their own data onto the web site via electronic case report forms (eCRFs). UNCCN personnel will coordinate and manage data for quality control assurance and integrity.

All data will be collected and entered into OnCore® by Clinical Research Associates (CRAs) from UNC LCCC and participating institutions. The investigators at each site will allow monitors to review all source documents supporting data entered into OnCore®. The UNCCN Data Coordinator can be reached at [contact] or [name].

As an investigator initiated study, this trial will also be audited by the Lineberger Cancer Center compliance committee every six or twelve months, depending on the participation of affiliate sites.

## **10.5 Adherence to the Protocol**

Except for an emergency situation in which proper care for the protection, safety, and well-being of the study patient requires alternative treatment, the study shall be conducted exactly as described in the approved protocol.

### **10.5.1 Emergency Modifications**

UNC and Affiliate investigators may implement a deviation from, or a change of, the protocol to eliminate an immediate hazard(s) to trial subjects without prior UNC or their respective institution's IRB/IEC approval/favorable opinion.

#### For Institutions Relying on UNC's IRB:

For any such emergency modification implemented, a UNC IRB modification form must be completed by UNC Research Personnel within five (5) business days of making the change.

#### For Institutions Relying on Their Own IRB:

For Affiliate investigators relying on their own institution's IRB, as soon as possible after the modification has been made, the implemented deviation or change and the reasons for it should be submitted to:

- To UNC Principal Investigator for agreement
- The Affiliate institution's IRB for review and approval. (Once IRB's response is received, this should be forwarded to the UNCCN Regulatory Associate).

### **10.5.2 Single Patient/Subject Exceptions**

Eligibility single subject exceptions are not permitted for Lineberger Comprehensive Cancer Center Investigator Initiated Trials under any circumstances. Other types of single subject exceptions may be allowed if proper regulatory review has been completed in accordance with Lineberger Comprehensive Cancer Center's Single Subject Exceptions Policy.

### **10.5.3 Other Protocol Deviations/Violations**

According to UNC's IRB, a protocol deviation is any unplanned variance from an IRB approved protocol that:

- Is generally noted or recognized after it occurs
- Has no substantive effect on the risks to research participants
- Has no substantive effect on the scientific integrity of the research plan or the value of the data collected

- Did not result from willful or knowing misconduct on the part of the investigator(s).

An unplanned protocol variance is considered a violation if the variance meets any of the following criteria:

- Has harmed or increased the risk of harm to one or more research participants.
- Has damaged the scientific integrity of the data collected for the study.
- Results from willful or knowing misconduct on the part of the investigator(s).
- Demonstrates serious or continuing noncompliance with federal regulations, State laws, or University policies.

If a deviation or violation occurs please follow the guidelines below:

For Institutions Relying on UNC's IRB:

**Protocol Deviations:** UNC or Affiliate personnel will record the deviation in OnCore®, and report to any sponsor or data and safety monitoring committee in accordance with their policies. Deviations should be summarized and reported to the IRB at the time of continuing review.

**Protocol Violations:** Violations should be reported by UNC personnel within one (1) week of the investigator becoming aware of the event using the same IRB online mechanism used to report Unanticipated Problems.

For Institutions Relying on Their Own IRB:

In addition to adhering to the policies regarding protocol compliance set forth by your institution's IRB, the following is also required:

**Protocol Deviations:** In the event a deviation from protocol procedures is identified, record the deviation in OnCore®.

**Protocol Violations:** Any protocol violation that occurs must be reported to your IRB per institutional policies and reported to the UNCCN Project Manager within 5 days. UNC-CH will determine if the violation affects the safety of the patient and integrity of the data. Once your institution's IRB response is received, please forward to the UNCCN Regulatory Associate.

### **Unanticipated Problems:**

#### UNC

Any events that meet the criteria for “Unanticipated Problems” as defined by UNC’s IRB must be reported by the Study Coordinator using the IRB’s web-based reporting system.

#### Affiliate Sites:

Any events that meet the criteria for “Unanticipated Problems (UPs)” as defined by UNC’s IRB must also be reported to the UNCCN Project Manager. The UNCCN Project Manager will report the event to the UNC IRB using the IRB’s web-based reporting system. Examples of such UPs include a lost or stolen laptop computer that contains sensitive study information.

### **10.6 Amendments to the Protocol**

Should amendments to the protocol be required, the amendments will be originated and documented by the Principal Investigator at UNC. It should also be noted that when an amendment to the protocol substantially alters the study design or the potential risk to the patient, a revised consent form might be required.

#### For Institutions Relying on UNC’s IRB:

The written amendment, and if required the amended consent form, must be sent to UNC’s IRB for approval prior to implementation.

#### For Institutions Relying on Their Own IRB:

Investigators must submit the UNC IRB approved amendment to their institution’s IRB for approval. For multi-center studies, any affiliate site must submit their informed consent revisions to the UNCCN Regulatory Associate prior to submission to their IRB.

### **10.7 Record Retention**

Study documentation includes all eCRFs, data correction forms or queries, source documents, Sponsor correspondence to Investigators, monitoring logs/letters, and regulatory documents (e.g., protocol and amendments, IRB correspondence and approval, signed patient consent forms).

Source documents include all recordings of observations or notations of clinical activities and all reports and records necessary for the evaluation and reconstruction of the clinical research study.

Government agency regulations and directives require that all study documentation pertaining to the conduct of a clinical trial must be retained by the study investigator. In the case of a study with a drug seeking regulatory approval and marketing, these documents shall be retained for at least two years after the

last approval of marketing application in an International Conference on Harmonization (ICH) region. In all other cases, study documents should be kept on file until three years after the completion and final study report of this investigational study.

#### **10.8 Obligations of Investigators**

The Principal Investigator is responsible for the conduct of the clinical trial at the site in accordance with Title 21 of the Code of Federal Regulations and/or the Declaration of Helsinki. The Principal Investigator is responsible for personally overseeing the treatment of all study patients. The Principal Investigator must assure that all study site personnel, including sub-investigators and other study staff members, adhere to the study protocol and all FDA/GCP/NCI regulations and guidelines regarding clinical trials both during and after study completion.

The Principal Investigator at each institution or site will be responsible for assuring that all the required data will be collected and entered into the eCRFs. Periodically, monitoring visits will be conducted and the Principal Investigator will provide access to his/her original records to permit verification of proper entry of data. At the completion of the study, all eCRFs will be reviewed by the Principal Investigator and will require his/her final signature to verify the accuracy of the data.

## 12.0 APPENDICES

### 12.1 Management Guideline for Cetuximab Skin Toxicity

#### Management of Grade 2 Rash

Skin lesions and symptoms	Eruption with papules (grade 2A) or pustules (grade 2B) covering <50% of body surface, with moderate symptoms, and that does not interfere with daily activities
Cetuximab dose modifications	No
Topical treatment	Antibiotics: clindamycin 1% gel, erythromycin 3% gel/cream, metronidazole 0.75%-1% cream/gel, twice/day until regression to grade 1 (avoid benzoyl peroxide products). Lesions of the scalp: erythromycin 2% lotion
Systemic treatment	Prevalence of papules (grade 2A): No Prevalence of pustules (grade 2B): Antibiotics: minocycline 100 mg per os once/day, doxycycline 100 mg per os once/day for ≥4 weeks and until the rash is symptomatic

#### Management of Grade 3 Rash

Skin lesions and symptoms	Eruption with papules (grade 3A) or pustules (grade 3B) covering >50% of body surface; severe symptoms that interfere with daily activities
Cetuximab dose modifications	First occurrence: delay cetuximab infusion for ≤21 days until the skin rash improves to grade ≤ 2. If there is an improvement, continue at 250 mg/m  . If there is no improvement, discontinue therapy. Second occurrence: delay cetuximab infusion for ≤21 days until the skin rash improves to grade ≤ 2. If there is an improvement, continue at reduced dose of 200 mg/m  . If there is no improvement, discontinue therapy. Third occurrence: delay cetuximab infusion for ≤21 days until the skin rash improves to grade ≤ 2. If there is improvement, continue at reduced dose of 150 mg/m  . If there is no improvement, discontinue therapy. Fourth occurrence: discontinue therapy definitively
Topical treatment	Antibiotics: clindamycin 1% gel, erythromycin 3% gel/cream, metronidazole 0.75-1% cream/gel, twice/day until regression to grade 1 (avoid benzoyl peroxide products). Lesions of the scalp: erythromycin 2% lotion
Systemic treatment	Antibiotics: minocycline 100 mg per os once/day, doxycycline 100 mg per os once/day for ≥4 weeks and until the rash is symptomatic Corticosteroids: methylprednisolone 0.4 mg/kg per os, prednisone 0.5 mg/kg per os, for up to 10 days
Systemic treatment in highly symptomatic/nonresponsive patients	Retinoids: isotretinoin 0.3-0.5 mg/kg per os Corticosteroids: methylprednisolone or dexamethasone i.v. Antihistamines: clorfenamine i.m./i.v. Antibiotics: amoxicillin/clavulanic acid, gentamicin i.v. Intravenous hydration

Reference: Carmine Pinto et al. The Oncologist 2011;16:228-238

**Management of Grade 4 Rash**

Skin lesions and symptoms	Generalized rash; severe symptoms that require emergency treatment
Cetuximab dose modifications	Discontinue therapy immediately and definitively
Topical treatment	Antibiotics: clindamycin 1% gel, erythromycin 3% gel/cream, metronidazole 0.75%–1% cream/gel, 2 times daily until regression to grade 1 (avoid benzoyl peroxide products). Lesions of the scalp: erythromycin 2% lotion
Systemic treatment	Retinoids: isotretinoin 0.3–0.5 mg/kg per os Corticosteroids: methylprednisolone, dexamethasone i.v. Antihistamines: clorfenamine i.m./i.v. Antibiotics: amoxicillin/clavulanic acid, gentamicin i.v. Intravenous hydration Hospitalization

Reference: Carmine Pinto et al. The Oncologist 2011;16:228-238

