### 5.3.2 Dose Modifications/Delays for Cetuximab (Rash)

Severe Acneiform Rash	Cetuximab Dosing	Outcome	Dose modification
1 st occurrence	Delay infusion 1 to 2 weeks	Improvement	Continue 250 mg/m 
		No improvement	Discontinue Cetuximab
2 nd occurrence	Delay infusion 1 to 2 weeks	Improvement	Reduce to 200 mg/m 
		No improvement	Discontinue Cetuximab
3 rd occurrence	Delay infusion 1 to 2 weeks	Improvement	Reduce to 150 mg/m 
		No improvement	Discontinue Cetuximab
4 th occurrence		Discontinue Cetuximab	

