### **5.6 Duration of Therapy**

Treatment may continue until:

- Disease progression
- Inter-current illness that prevents further administration of treatment

- Unacceptable adverse event(s)
- Pregnancy
- Patient decides to withdraw from study treatment, **OR**
- General or specific changes in the patient's condition render the patient unacceptable for further treatment in the judgment of the investigator.
- Subject completes maximum number of treatment cycles allowed per protocol
- Subject is lost to follow up

It is anticipated that subjects will receive on average 4 to 6 months of study treatment.

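### Section 5.3.2 and Appendix 12.1 set different hold and recovery rules for cetuximab after severe rash, and no text says which prevails

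*Combined protocol and SAP*

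**What the plan says.** The protocol states cetuximab dose rules for rash in two places.

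**Section 5.3.2.** The table has one trigger, "Severe Acneiform Rash". At the first, second and third occurrence the action is "Delay infusion 1 to 2 weeks". With improvement, cetuximab goes on at 250, 200 and 150 mg/m² respectively; without improvement, it is discontinued. A fourth occurrence ends cetuximab. The table gives no CTCAE grade, does not say how much improvement is needed, has no grade 4 row and does not mention Appendix 12.1.

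**Appendix 12.1.** Each grade has its own table, with a row for cetuximab dose modification.
- Grade 3 is described by extent and by "severe symptoms that interfere with daily activities". The rule at each of the first three occurrences is "delay cetuximab infusion for ≤21 days until the skin rash improves to grade ≤ 2", followed by 250, 200 and 150 mg/m². Then: "Fourth occurrence: discontinue therapy definitively".
- Grade 4 is described as "Generalized rash; severe symptoms that require emergency treatment". The rule is "Discontinue therapy immediately and definitively".

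**Links between the two.** The end of Section 5.4.1 sends the reader to Appendix 12.1 for skin toxicity of grade 2 or higher. Section 6.2.2 names Section 5.3.2 for dose modification, and Section 5.4.1 and Appendix 12.1 for prophylaxis and toxicity management. Neither place says which rule governs if they differ. Section 7.1.5 has adverse events assessed by CTCAE 4.03.

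**The concern.** Both sections direct the same decision: whether, when and at what dose cetuximab restarts after a serious rash. They use different time limits, and only one sets a graded recovery level. Two sites can therefore each follow a written rule and treat the same patient differently. One patient may lose cetuximab a week earlier than another; one may be re-dosed while the rash is still grade 3.

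There is a second, weaker worry. The Section 5.3.2 trigger is ungraded, and Appendix 12.1 uses the word severe for the symptoms of both grade 3 and grade 4, so the label does not by itself keep grade 4 out of the ladder. At stake are patient safety and uniform conduct across sites in a multicenter trial.

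**Working it through.** There is no sample-size, power or alpha figure to reproduce. The check sets the two rules side by side.

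**Step 1: which grade does Section 5.3.2 address?** Its dose steps (250, 200, 150 mg/m², stop at the fourth occurrence) are those of the Appendix 12.1 grade 3 table. Acneiform also fits the papules and pustules of the grade 3 description better than the generalized rash of grade 4. The likely meaning is grade 3, though no text says so.

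**Step 2: compare the grade 3 rules, counting days from the start of the hold.**
- Section 5.3.2: maximum hold = 2 weeks × 7 = 14 days; recovery needed = improvement, ungraded.
- Appendix 12.1: maximum hold = 21 days; recovery needed = grade 2 or lower.
- Difference in maximum hold = 21 − 14 = 7 days = one weekly infusion.

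**Step 3: apply both rules to the same patient, first occurrence.**

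| Course of the rash | Section 5.3.2 | Appendix 12.1 |
|---|---|---|
| Grade 2 or lower by day 14 | Resume 250 mg/m² | Resume 250 mg/m² |
| Improved by day 14, still grade 3 | Resume 250 mg/m² | Not yet; hold may run to day 21 |
| No improvement by day 14, grade 2 or lower on days 15 to 21 | Discontinue | Resume 250 mg/m² |
| No improvement by day 21 | Discontinue, by day 14 | Discontinue, by day 21 |

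Rows 2 and 3 give different actions. The same mismatch recurs at the second and third occurrences, at 200 and 150 mg/m². At the fourth, both sections stop cetuximab.

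**Step 4: a first grade 4 rash that improves.**

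| Meaning of severe in Section 5.3.2 | Section 5.3.2 | Appendix 12.1 |
|---|---|---|
| Grade 3 only (likely) | No action stated | Permanent stop |
| Grade 3 and grade 4 | Hold, then weekly 250 mg/m² resumes | Permanent stop |

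On the broad reading, dosing resumes at 250/250 = 100% of the maintenance dose and continues weekly until another occurrence or another reason to stop.

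**Step 5: compare with the rest of Section 5.3.** Of its four dose-action tables, three (hematologic and non-hematologic toxicity in Section 5.3.1, infusion reactions in Section 5.3.3) are set out by CTCAE grade and state an action that covers grade 4. The rash table does neither. This measures consistency of format, not risk.

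**Step 6: frequency.** Section 6.2.2 gives no rash rate for cetuximab. The only rash rate, in Section 6.1.6 (grade 3 in 7 of 872 patients, grade 4 in 0 of 872), comes from palbociclib studies and cannot stand in for it. No event probability is computed.

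**The case against.** A reader might infer that the protocol tells sites to re-dose after a grade 4 rash. The documents do not support that. Appendix 12.1 is part of the protocol and orders a permanent stop at grade 4; Section 5.4.1 points to it in bold; the Section 5.3.2 ladder matches grade 3. A site that uses Section 5.3.2 for grade 3 and Appendix 12.1 for grade 4 breaks no rule on grade 4. Section 5.6 and the cetuximab dosing text in Section 6.2 also end treatment for unacceptable toxicity. All of this stands, and it reduces the grade 4 issue to an ambiguity. What it leaves is that Section 6.2.2 sends the reader to Section 5.3.2 for dose modification, and that the general stop for unacceptable toxicity rests on judgment whereas the Appendix 12.1 stop is automatic.

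On grade 3, it can be said that a hold of 1 to 2 weeks fits inside a limit of 21 days, so a site can meet both limits by using the shorter one. That is right for the time limit alone. It fails on recovery. At day 14, with a rash that has improved but is still grade 3, Section 5.3.2 says resume and Appendix 12.1 says keep holding: resuming departs from Appendix 12.1, and holding longer departs from Section 5.3.2. Section 10.5 requires conduct exactly as the protocol describes, which does not help where two rules differ.

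It is also fair that the rate of such rashes is unknown, so no number supports a high priority.

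**Conclusion.** The concern holds for grade 3. On the likely reading, the two sections differ by 7 days (one weekly infusion) in the maximum hold and in the recovery needed before re-dosing, and they give different actions in two identifiable courses of the same rash. This assumes that severe in Section 5.3.2 means grade 3 and that the end of the 2-week delay is the point at which lack of improvement ends cetuximab.

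The grade 4 point is secondary: the text can be read as allowing weekly 250 mg/m² to resume, but that is the less natural reading. Nor should a reader infer bias in the 4-month disease control rate; none is claimed. This is a low-cost safety clarification that should be made.

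**What to change.** In Section 5.3.2:
- replace the word severe with grade 3;
- add a row stating that at grade 4 cetuximab is discontinued immediately and permanently;
- add a cross-reference to Appendix 12.1.

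In both Section 5.3.2 and Appendix 12.1, state one maximum hold for grade 3 and one recovery criterion. The sponsor should choose 14 or 21 days. Grade 2 or lower is the only graded criterion in the documents and is the natural choice. This has to go in the same amendment: relabelling the ladder as grade 3 alone would put two hold limits in open conflict for the same grade.

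The cost is a short amendment, with the IRB approval that Section 10.6 requires, and a memo to sites. Sample size, visit schedule and endpoints do not change.

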### 12.3 ECOG Performance Status

Grade	Description
0	Normal activity. Fully active, able to carry on all pre-disease performance without restriction.
1	Symptoms, but ambulatory. Restricted in physically strenuous activity, but ambulatory and able to carry out work of a light or sedentary nature (e.g., light housework, office work).
2	In bed <50% of the time. Capable of only limited self-care, confined to bed or chair more than 50% of waking hours.
3	In bed >50% of the time. Capable of only limited self-care, confined to bed or chair more than 50% of waking hours.
4	100% bedridden. Completely disabled. Cannot carry on any self-care. Totally confined to bed or chair.
5	Dead.

[figure not shown]
\* As published in Am. J. Clin. Oncol.: *Oken, M.M., Creech, R.H., Tormey, D.C., Horton, J., Davis, T.E., McFadden, E.T., Carbone, P.P. Toxicity and Response Criteria of the Eastern Cooperative Oncology Group. Am J Clin Oncol 5:649-655, 1982.* The Eastern Cooperative Oncology Group, Robert Comis M.D., Group Chair.

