### 4.1 Inclusion Criteria

- 4.1.1** Written informed consent obtained to participate in the study and HIPAA authorization for release of personal health information.
- 4.1.2** Age  $\geq$  18 years at the time of consent.
- 4.1.3** ECOG Performance Status of 0-2
- 4.1.4** Histologically-confirmed metastatic CRC
- 4.1.5** Measurable disease according to RECIST v1.1 for solid tumors.
- 4.1.6** Documented wild-type in KRAS and NRAS (codons 12, 13, 59, 61, 117, and 146) and in BRAF codon 600, based on tumor tissue taken from primary or metastatic site and tested for biomarkers
- 4.1.7** Previously treated with at least two prior regimens of systemic chemotherapy for metastatic or locally advanced, unresectable disease, including fluoropyrimidines (5-fluorouracil and/or capecitabine), oxaliplatin, and irinotecan.
  - A maintenance regimen of 5-fluorouracil or capecitabine, with or without bevacizumab, should not be counted as a separate line of treatment
  - For patients who experienced disease recurrence during or within 6 months of completion of adjuvant chemotherapy with fluoropyrimidine and oxaliplatin, only one regimen of systemic chemotherapy for metastatic disease is required
- 4.1.8** Demonstrate adequate organ function as defined in the table below; all screening labs to be obtained prior to initiating study medications.

System	Laboratory Value
Hematological*	
Hemoglobin (Hgb)	$\geq 9$ g/dL
Absolute Neutrophil Count (ANC)	$\geq 1500/\text{mm}^3$
Platelets	$\geq 100,000/\text{mm}^3$
Renal*	

Creatinine OR Calculated creatinine clearance	$\leq 1.5 \times \text{ULN}$ $\geq 60 \text{ mL/min}$ by Cockcroft-Gault formula
Hepatic*	
Bilirubin	$\leq 1.0 \times \text{upper limit of normal (ULN)}$
Aspartate aminotransferase (AST)	$\leq 3 \times \text{ULN}$ OR $\leq 5 \times \text{ULN}$ (if liver metastases present)
Alanine aminotransferase (ALT)	$\leq 3 \times \text{ULN}$ OR $\leq 5 \times \text{ULN}$ (if liver metastases present)

\*Note: Hematology and other lab parameters that are  $\leq$  grade 2 BUT still meet criteria for study entry are allowed. Furthermore, changes in laboratory parameters during the study should not be considered adverse events unless they meet criteria for dose modification(s) of study medication outlined by the protocol and/or worsen from baseline during therapy.

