### **7.1.4 Physical Examination**

A complete physical examination including height (at screening only), weight, performance status per Eastern Cooperative Oncology Group (ECOG ) criteria (provided in Appendix 12.3) and **vital signs** (i.e., temperature, heart rate, blood pressure) will be performed by either the investigator or a sub-investigator who is a physician at Screening and on day 1 of the first and second treatment cycle. An abbreviated physical exam may be performed at all other visits and should include vital signs and ECOG performance status.

New abnormal physical exam findings must be documented and will be followed by a physician or other qualified staff at the next scheduled visit.

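### Appendix 12.3 contradicts itself at ECOG grade 2, the upper limit for entry, so a patient who fits the grade 3 description could be scored as eligible

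*Combined protocol and SAP*

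**What the plan says.** Section 4.1.3 sets the entry requirement: "ECOG Performance Status of 0-2". Section 7.1.4 includes performance status in the physical examination, to be scored by the Eastern Cooperative Oncology Group criteria, "provided in Appendix 12.3". No other section describes the grades.

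In Appendix 12.3 each row from grade 0 to grade 3 has a short opening phrase and then a fuller description. Grade 2 reads: "In bed <50% of the time. Capable of only limited self-care, confined to bed or chair more than 50% of waking hours". Grade 3 reads: "In bed >50% of the time. Capable of only limited self-care, confined to bed or chair more than 50% of waking hours".

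Section 10.5 requires the study to be run as the approved protocol describes, and Section 10.5.2 closes off discretion at entry: "Eligibility single subject exceptions are not permitted for Lineberger Comprehensive Cancer Center Investigator Initiated Trials under any circumstances".

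**The concern.** Grade 2 is the last eligible grade and grade 3 the first ineligible one. If the protocol's scale does not separate the two cleanly, criterion 4.1.3 has no single meaning for patients near that line. Because eligibility exceptions are barred, the score alone decides whether such a patient enters.

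Two things are at stake. The first is patient selection: the protocol could be read as admitting someone whom an ECOG limit of 2 is meant to keep out. The second is consistency: the trial is multicentre, and two sites could classify the same patient differently, each with support from the protocol text.

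**Working it through.** No formula applies, so the check is a comparison of the text.

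**Step 1: compare the two rows.** The opening phrases differ only in the sign, < for grade 2 and > for grade 3. The descriptive sentences that follow are identical, 16 words out of 16. That sentence agrees with the grade 3 opening phrase and conflicts with the grade 2 one.

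**Step 2: ask whether both parts of the grade 2 row can hold at once.** Read literally, they can. The opening phrase concerns time in bed; the sentence concerns waking time in bed or a chair. A patient who sits in a chair most of the day but is in bed for less than half the time satisfies both. This does not rescue the row, because the same patient also satisfies the grade 3 sentence.

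**Step 3: apply the rows to three kinds of patient.**

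- In bed more than half the time: the opening phrases give grade 3. The sentence fits grades 2 and 3 equally.
- In bed less than half the time, but in bed or a chair for most of the waking day: the opening phrases give grade 2. The sentence again fits both grades.
- In bed or a chair for less than half the waking day, but not well enough for grade 1: only the opening phrase of grade 2 fits. Neither the grade 2 nor the grade 3 sentence describes this patient.

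The sentence therefore never distinguishes grade 2 from grade 3. Only the opening phrase does.

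**Step 4: trace the row to a decision.** Criterion 4.1.3 uses grade 2 as the limit, Section 7.1.4 names Appendix 12.3 as where the scale is found, and no other section offers a competing definition. The row is thus part of the working eligibility definition, not background.

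**Step 5: look for an effect on the design.** Section 9.2 sets the rules from null and target disease control rates (40% and 65% in Cohort A, 33% and 60% in Cohort B). Performance status enters none of them. It is not among the endpoints in Sections 3.1 and 3.2, and the visible text of Section 9.3 names no analysis that uses it.

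**The case against.** The strongest reply is that the opening phrases still separate the grades. An assessor who reads them first would score a patient in bed more than half the time as grade 3 and exclude that patient. There are further safeguards. Section 7.1.4 has the screening examination done by a physician and names the ECOG criteria themselves, with the appendix as a copy. The appendix cites the publication behind the scale. Section 10.3 has source documents reviewed to confirm eligibility before registration. Criterion 4.2.9 excludes severe uncontrolled comorbidity. On this view the row is a copying slip that oncology staff would see through.

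Most of that stands, and it limits the likely harm. It does not correct the row. A reviewer checking source documents against the protocol meets the same contradiction as the assessor.

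The table was also read from PDF by a program. Copying a complete sentence into the matching cell of the next row is not a typical extraction fault, but the page should be checked first.

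A reader might infer more than the documents support:

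- That grade 3 patients would be eligible under the protocol. The row makes this possible; the opening phrase still points the other way.
- That less fit patients would be compared with null rates set for fitter ones. Section 9.2 gives the sources of the nulls, a phase III study for Cohort A and a retrospective subgroup for Cohort B, but no ECOG range for either.
- That the loss in disease control rate can be estimated. The documents give neither the number of patients who might be misclassified nor a rate for them. If such patients do worse, which is an assumption, the effect would count against the regimen rather than raise the chance of a false positive.
- That repeated ECOG scores during treatment would damage an analysis. No visible analysis uses them, although part of the exploratory text is redacted.

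**Conclusion.** The point holds as an internal contradiction in an operative eligibility definition. It concerns one row of one appendix, and that row sits at the entry cut-off. The conclusion is that a patient confined for more than half the waking day could be scored as grade 2 and enrolled, and that sites could differ; it is not that this would happen.

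No numerical size can be given. The sample sizes, stage boundaries, endpoints and planned analyses do not change. The case for correction rests on clear eligibility and patient selection, not on any calculated loss of power or bias. It assumes that the extracted table matches the original page.

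**What to change.** Check the original page of Appendix 12.3. If it reads as extracted, revise the grade 2 description so that it agrees with its own opening phrase, and verify it against the publication cited beneath the table. That publication is not among the documents reviewed here, so no replacement wording is offered. Leave the grade 3 row unchanged.

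The cost is a one-line correction in an amendment. Under Section 10.6 it needs approval from the coordinating institution's IRB and, at sites that rely on their own, the local IRB, so it is best bundled with the next planned amendment. No change to design, sample size or analysis follows.
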